#### 4.1.3 Subject Exclusion Criteria

The subject must be excluded from participating in the trial if the subject:

1. Is currently participating and receiving study therapy or has participated in a study of an investigational agent and received study therapy or used an investigational device within 4 weeks of the first dose of treatment.

Pembrolizumab (MK-3475), [name], HUMC

2. Has a diagnosis of immunodeficiency or is receiving systemic steroid therapy or any other form of immunosuppressive therapy within 7 days prior to the first dose of trial treatment. The use of physiologic doses of corticosteroids may be used at the investigator's discretion.
3. Has received an allogeneic stem cell transplant.
4. Has received any myeloma-directed therapy after ASCT.
5. Has a known history of active TB (Bacillus Tuberculosis)
6. Hypersensitivity to pembrolizumab or any of its excipients.
7. Progressive disease from autologous transplantation at the time of screening. See Appendix 11.5 for criteria
8. Has known active central nervous system (CNS) metastases and/or carcinomatous meningitis. Subjects with previously treated brain metastases may participate provided they are stable (without evidence of progression by imaging for at least four weeks prior to the first dose of trial treatment and any neurologic symptoms have returned to baseline), have no evidence of new or enlarging brain metastases, and are not using steroids for at least 7 days prior to trial treatment. This exception does not include carcinomatous meningitis which is excluded regardless of clinical stability.
9. Has active autoimmune disease that has required systemic treatment in the past 2 years (i.e. with use of disease modifying agents, corticosteroids or immunosuppressive drugs). Replacement therapy (eg., thyroxine, insulin, or physiologic corticosteroid replacement therapy for adrenal or pituitary insufficiency, etc.) is not considered a form of systemic treatment.
10. Has a history of (non-infectious) pneumonitis that required steroids or current pneumonitis.
11. Has an active infection requiring intravenous systemic therapy.
12. Has a history or current evidence of any condition, therapy, or laboratory abnormality that might confound the results of the trial, interfere with the subject's participation for the full duration of the trial, or is not in the best interest of the subject to participate, in the opinion of the treating investigator.

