##### **4.2.1.2 Dose Modification**

Adverse events (both non-serious and serious) associated with pembrolizumab exposure may represent an immunologic etiology. These adverse events may occur shortly after the first dose or several months after the last dose of treatment. Pembrolizumab must be withheld for drug-related toxicities and severe or life-threatening AEs as per Table 3 below. See Section 4.6.1 and Events of Clinical Interest Guidance Document for supportive care guidelines, including use of corticosteroids.

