**Table 3a:**
**Dose Modification Guidelines for Pembrolizumab Drug-Related Adverse Events**

Toxicity	Hold Treatment For Grade	Timing for Restarting Treatment	Discontinue Subject
Diarrhea/Colitis	2-3	Toxicity resolves to Grade 0-1.	Toxicity does not resolve within 12 weeks of last dose or inability to reduce corticosteroid to 10 mg or less of prednisone or equivalent per day within 12 weeks.
	4	Permanently discontinue	Permanently discontinue
AST, ALT, or Increased Bilirubin	2	Toxicity resolves to Grade 0-1	Toxicity does not resolve within 12 weeks of last dose.
	3-4	Permanently discontinue (see exception below) 	Permanently discontinue
Type 1 diabetes mellitus (if new onset) or Hyperglycemia	T1DM or 3-4	Hold pembrolizumab for new onset Type 1 diabetes mellitus or Grade 3-4 hyperglycemia associated with evidence of beta cell failure.	Resume pembrolizumab when patients are clinically and metabolically stable.
Hypophysitis	2-3	Toxicity resolves to Grade 0-1	Toxicity does not resolve within 12 weeks of last dose or inability to reduce corticosteroid to 10 mg or less of prednisone or equivalent per day within 12 weeks.
	4	Permanently discontinue	Permanently discontinue
Hyperthyroidism	3	Toxicity resolves to Grade 0-1	Toxicity does not resolve within 12 weeks of last dose or inability to reduce corticosteroid to 10 mg or less of prednisone or equivalent per day within 12 weeks.
	4	Permanently discontinue	Permanently discontinue
Hypothyroidism	2-4	Therapy with pembrolizumab can be continued while treatment for the thyroid disorder is instituted	Therapy with pembrolizumab can be continued while treatment for the thyroid disorder is instituted.
Infusion Reaction	3-4	Permanently discontinue	Permanently discontinue
Renal Failure or Nephritis	2	Toxicity resolves to Grade 0-1	Toxicity does not resolve within 12 weeks of last dose or inability to reduce corticosteroid to 10 mg or less of prednisone or equivalent per day within 12 weeks.
	3-4	Permanently discontinue	Permanently discontinue
All Other Drug-Related Toxicity 	3 or Severe	Toxicity resolves to Grade 0-1	Toxicity does not resolve within 12 weeks of last dose or inability to reduce corticosteroid to 10 mg or less of prednisone or equivalent per day within 12 weeks.
	4	Permanently discontinue	Permanently discontinue

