**Note: Permanently discontinue for any severe or Grade 3 drug-related AE that recurs or any life-threatening event.**

 For patients with liver metastasis who begin treatment with Grade 2 AST or ALT, if AST or ALT increases by greater than or equal to 50% relative to baseline and lasts for at least 1 week then patients should be discontinued.

 Patients with intolerable or persistent Grade 2 drug-related AE may hold study medication at physician discretion. Permanently discontinue study drug for persistent Grade 2 adverse reactions for which treatment with study drug has been held, that do not recover to Grade 0-1 within 12 weeks of the last dose.

Table 3b:  
Dose-Modification Guidelines for Hematological Toxicity

Toxicity	Grade	Hold Treatment (Y/N)	Timing for restarting treatment	Dose/Schedule for restarting treatment 1	Discontinue Subject (after consultation with Sponsor)
Hematological Toxicity	1, 2, 3	No	N/A	N/A	N/A
	4	Yes	Toxicity resolves to Grade 0-1 or baseline	May decrease dose to next dose level below	Toxicity does not resolve within 4 weeks of last infusion  Permanent discontinuation should be considered for any severe or life-threatening event

Dosing interruptions are permitted in the case of medical / surgical events or logistical reasons not related to study therapy (e.g., elective surgery, unrelated medical events, patient vacation, and/or holidays). Subjects should be placed back on study therapy within 3 weeks of the scheduled interruption, unless otherwise discussed with the Sponsor. The reason for interruption should be documented in the patient's study record.

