#### **4.5.2 Prohibited Concomitant Medications**

Subjects are prohibited from receiving the following therapies during the Screening and Treatment Phase (including retreatment for post-complete response relapse) of this trial:

- Antineoplastic systemic chemotherapy or biological therapy
- Immunotherapy not specified in this protocol
- Chemotherapy not specified in this protocol
- Investigational agents other than pembrolizumab
- Radiation therapy
  - Note: Radiation therapy to a symptomatic solitary lesion or to the brain may be allowed at the investigator's discretion.
- Live vaccines within 30 days prior to the first dose of trial treatment and while participating in the trial. Examples of live vaccines include, but are not limited to, the following: measles, mumps, rubella, varicella/zoster, yellow fever, rabies, BCG, and typhoid vaccine.
- Systemic glucocorticoids for any purpose other than to modulate symptoms from an event of clinical interest of suspected immunologic etiology. The use of physiologic doses of corticosteroids may be approved after consultation with the Sponsor.

Subjects who, in the assessment by the investigator, require the use of any of the aforementioned treatments for clinical management should be removed from the trial. Subjects may receive other medications that the investigator deems to be medically necessary.

The Exclusion Criteria describes other medications which are prohibited in this trial.

There are no prohibited therapies during the Post-Treatment Follow-up Phase.

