## 4.6 Rescue Medications & Supportive Care

### 4.6.1 Supportive Care Guidelines

Subjects should receive appropriate supportive care measures as deemed necessary by the treating investigator. Suggested supportive care measures for the management of adverse events with potential immunologic etiology are outlined below and in greater detail in the ECI guidance document. Where appropriate, these guidelines include the use of oral or intravenous treatment with corticosteroids as well as additional anti-inflammatory agents if symptoms do not improve with administration of corticosteroids. Note that several courses of steroid tapering may be necessary as symptoms may worsen when the steroid dose is decreased. For each disorder, attempts should be made to rule out other causes such as metastatic disease or bacterial or viral infection, which might require additional supportive care. The treatment guidelines are intended to be applied when the investigator determines the events to be related to pembrolizumab.

Note: if after the evaluation the event is determined not to be related, the investigator is instructed to follow the ECI reporting guidance but does not need to follow the treatment guidance (as outlined in the ECI guidance document). Refer to Section 4.2.1 for dose modification.

It may be necessary to perform conditional procedures such as bronchoscopy, endoscopy, or skin photography as part of evaluation of the event. Suggested conditional procedures, as appropriate, can be found in the ECI guidance document.

- **Pneumonitis:**

- For **Grade 2 events**, treat with systemic corticosteroids. When symptoms improve to Grade 1 or less, steroid taper should be started and continued over no less than 4 weeks.
- For **Grade 3-4 events**, immediately treat with intravenous steroids. Administer additional anti-inflammatory measures, as needed.
- Add prophylactic antibiotics for opportunistic infections in the case of prolonged steroid administration.

- **Diarrhea/Colitis:**

Subjects should be carefully monitored for signs and symptoms of enterocolitis (such as diarrhea, abdominal pain, blood or mucus in stool, with or without fever) and of bowel perforation (such as peritoneal signs and ileus).

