#### 4.8 Subject Withdrawal/Dis continuation Criteria

Subjects may withdraw consent at any time for any reason or be dropped from the trial at the discretion of the investigator should any untoward effect occur. In addition, a subject may be withdrawn by the investigator or the Sponsor if enrollment into the trial is inappropriate, the

trial plan is violated, or for administrative and/or other safety reasons. Specific details regarding discontinuation or withdrawal are provided in Section 6.1.4 – Other Procedures.

A subject must be discontinued from the trial for any of the following reasons:

- The subject or legal representative (such as a parent or legal guardian) withdraws consent.
- Confirmed disease progression, including biochemical disease progression, and radiographic disease progression
- Unacceptable adverse experiences as described in Section 4.2.1.
- Intercurrent illness that prevents further administration of treatment
- Investigator's decision to withdraw the subject
- The subject has a confirmed positive serum pregnancy test
- Noncompliance with trial treatment or procedure requirements
- The subject is lost to follow-up
- Administrative reasons

The End of Treatment and Follow-up visit procedures are listed in Section 5 (Protocol Flow Chart). After the end of treatment, each subject will be followed for 30 days for adverse event monitoring (serious adverse events will be collected for 90 days after the end of treatment as described). Subjects who discontinue for reasons other than progressive disease will have post-treatment follow-up for disease status until disease progression, initiating a non-study cancer treatment, withdrawing consent or becoming lost to follow-up. After documented disease progression each subject will be followed by telephone for overall survival until death, withdrawal of consent, or the end of the study, whichever occurs first.

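### Grade 2 pneumonitis is treated with steroids but carries no mandatory pembrolizumab hold, unlike the four other toxicities given steroids at Grade 2

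*Combined protocol and SAP*

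**What the plan says.** Section 4.2.1.2 sets the governing rule: "Pembrolizumab must be withheld for drug-related toxicities and severe or life-threatening AEs as per Table 3 below". Table 3a then lists eight named rows: diarrhea/colitis; AST, ALT or bilirubin; type 1 diabetes or hyperglycemia; hypophysitis; hyperthyroidism; hypothyroidism; infusion reaction; and renal failure or nephritis. A catch-all row, "All Other Drug-Related Toxicity", follows. It requires a hold at Grade 3 or severe and permanent discontinuation at Grade 4. For Grade 2 events in that row, footnote 2 says: "Patients with intolerable or persistent Grade 2 drug-related AE may hold study medication at physician discretion".

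Section 4.6.1 sets no hold rule of its own. It says: "Refer to Section 4.2.1 for dose modification". For Grade 2 pneumonitis its instruction is to "treat with systemic corticosteroids. When symptoms improve to Grade 1 or less, steroid taper should be started", with the taper lasting at least 4 weeks.

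Elsewhere the protocol takes pneumonitis seriously. Exclusion 10 in Section 4.1.3 bars a patient who "Has a history of (non-infectious) pneumonitis that required steroids or current pneumonitis", and Appendix 11.6 makes pneumonitis an event of clinical interest (ECI) from Grade 2.

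**The concern.** Where the protocol considers a Grade 2 toxicity serious enough for corticosteroids, it otherwise requires pembrolizumab to be held until the event resolves to Grade 0-1. Pneumonitis is the one exception, and the protocol gives no reason for it. A patient with active Grade 2 pneumonitis could receive the next infusion without any departure from the written rule, and two physicians could handle the same event differently. What is at stake is patient safety during treatment, not the efficacy analysis.

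**Working it through.** No formula applies to the main point. The check sets Section 4.6.1 beside Table 3a and then looks for a hold rule anywhere else.

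**Step 1. Steroids at Grade 2 against the hold at Grade 2.**

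| Heading in 4.6.1 | Steroid at Grade 2? | Table 3a at Grade 2 |
|---|---|---|
| Pneumonitis | Yes | No row; discretionary under the catch-all and footnote 2 |
| Diarrhea/colitis | Yes, if it lasts more than 3 days | Mandatory hold (Grades 2-3) |
| Hypophysitis | Yes | Mandatory hold (Grades 2-3) |
| Hepatic | Yes | Mandatory hold (Grade 2) |
| Renal | Yes | Mandatory hold (Grade 2) |
| Type 1 diabetes/hyperglycemia | No | Named row; hold for new-onset type 1 diabetes or Grade 3-4 hyperglycemia |
| Hyper-/hypothyroidism | No | Two named rows; hyperthyroidism held from Grade 3, hypothyroidism continues |
| Infusion reaction | Not listed at Grade 2 | Named row; discontinue at Grades 3-4 |

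Five headings give steroids at Grade 2, and 4 of the 5 have a mandatory Grade 2 hold. Of the 8 headings, 7 have a named row (the thyroid heading has two, which gives the eight named rows). Pneumonitis is the exception in both counts.

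**Step 2. Could the catch-all row still force a hold at Grade 2?** Its threshold is Grade 3 or severe. Table 11 describes Grade 2 as moderate and Grade 3 as severe, so a Grade 2 event does not meet it.

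**Step 3. Does anything else force a hold?**

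- Section 4.5.2 prohibits "Systemic glucocorticoids for any purpose other than to modulate symptoms from an event of clinical interest of suspected immunologic etiology". Steroids for immune-related pneumonitis fall within the exception, so giving them does not remove the patient.
- Section 4.5 says only that discontinuation may be needed when a prohibited medication is indicated.
- Section 4.8 lists "Unacceptable adverse experiences as described in Section 4.2.1", which leads back to the section with the gap.
- Section 6.2.3.2 requires assessment for ECIs before each dose and a report to the sponsor within 24 hours. It does not require the dose to be held.
- Section 4.1.3 concerns entry only, and Appendix 11.6 concerns reporting only.

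**Step 4. How often does the question arise within a patient?** Infusions fall on Day 1 of four 21-day cycles: days 1, 1 + 21 = 22, 22 + 21 = 43 and 43 + 21 = 64. Onset after dose 1, 2, 3 or 4 leaves 3, 2, 1 or 0 infusions. The taper alone lasts at least 4 × 7 = 28 days, longer than the dosing interval even with the 3-day window (21 + 3 = 24 days). If steroids start before the next scheduled infusion, that infusion therefore falls due while the patient is still taking them. The decision whether to dose has to be made, and the table does not make it.

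**Step 5. Grades 3-4.** Under the catch-all, Grade 3 is held and Grade 4 is discontinued. This matches colitis and hypophysitis and is less strict than hepatic and renal, which discontinue at Grade 3. The note to the table also requires discontinuation if a Grade 3 event recurs. The inconsistency is therefore confined to Grade 2.

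**The case against.** The strongest objection is that everything rests on one absent row in a table read from a PDF. A row dropped cleanly in conversion would leave no gap, and the type 1 diabetes row looks shifted by a column, so the table may not be intact. This stands as a caveat. The text does run without a break from the infusion reaction row to the renal row, but only the source can settle it.

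Second, the separate ECI guidance document is not available. Section 4.6.1 says it covers management in more detail, so it may address dosing. This stands in part. However, Section 4.2.1.2 cites that document for supportive care and Table 3 for withholding, and 4.6.1 refers back to 4.2.1 for dose modification.

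Third, the practical gap is narrow. A physician could readily call pneumonitis that is still Grade 2 at the next Day 1 persistent and hold the dose; ECI assessment and prompt reporting add scrutiny; and Section 4.5 offers another ground to stop. Because dosing would resume at Grade 0-1 under the proposed row, the change affects only patients still at Grade 2 on an infusion day whom the physician would otherwise dose. That limits the size of the problem. But none of these safeguards is mandatory, and the protocol did not leave the decision to judgment for the other four toxicities.

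Fourth, the steroid measures in 4.6.1 are presented as suggestions, and the colitis steroid depends on duration. This loosens the comparison slightly. The Grade 2 holds in Table 3a are unconditional for all four comparators.

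**Conclusion.** The concern holds. On the text available, pneumonitis is the only one of five toxicities given steroids at Grade 2 that has no mandatory Grade 2 hold, and the only one of eight headings in 4.6.1 without a named row in Table 3a. Following the written rule permits pembrolizumab during active Grade 2 pneumonitis.

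Exposure is limited to at most three remaining infusions per patient, in a trial of about 43. The documents give no incidence for Grade 2 pneumonitis, so no expected number of affected patients is offered. The point should be fixed. Confidence is medium, because the conclusion assumes that no pneumonitis row was lost in conversion and that the ECI guidance document does not impose a hold.

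**What to change.** Check the source of Table 3a for a pneumonitis row. If there is one, the point falls away. If there is none, add a row that:

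- requires a hold at Grade 2;
- allows restart when the event resolves to Grade 0-1;
- discontinues the patient if the event has not resolved within 12 weeks of the last dose, or if corticosteroids cannot be brought down to 10 mg per day or less of prednisone or equivalent within 12 weeks.

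These are the terms already used in the colitis, hypophysitis and renal rows. The sponsor's clinical team should state the Grade 3-4 and recurrence rules in the same row, so that pneumonitis no longer depends on the catch-all. The cost is one table row in an amendment. The downside is a few more held doses in a four-dose schedule.

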**Note: Permanently discontinue for any severe or Grade 3 drug-related AE that recurs or any life-threatening event.**

 For patients with liver metastasis who begin treatment with Grade 2 AST or ALT, if AST or ALT increases by greater than or equal to 50% relative to baseline and lasts for at least 1 week then patients should be discontinued.

 Patients with intolerable or persistent Grade 2 drug-related AE may hold study medication at physician discretion. Permanently discontinue study drug for persistent Grade 2 adverse reactions for which treatment with study drug has been held, that do not recover to Grade 0-1 within 12 weeks of the last dose.

Table 3b:  
Dose-Modification Guidelines for Hematological Toxicity

Toxicity	Grade	Hold Treatment (Y/N)	Timing for restarting treatment	Dose/Schedule for restarting treatment 1	Discontinue Subject (after consultation with Sponsor)
Hematological Toxicity	1, 2, 3	No	N/A	N/A	N/A
	4	Yes	Toxicity resolves to Grade 0-1 or baseline	May decrease dose to next dose level below	Toxicity does not resolve within 4 weeks of last infusion  Permanent discontinuation should be considered for any severe or life-threatening event

Dosing interruptions are permitted in the case of medical / surgical events or logistical reasons not related to study therapy (e.g., elective surgery, unrelated medical events, patient vacation, and/or holidays). Subjects should be placed back on study therapy within 3 weeks of the scheduled interruption, unless otherwise discussed with the Sponsor. The reason for interruption should be documented in the patient's study record.

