### Pembrolizumab (MK-3475)

Pembrolizumab (MK-3475) will be administered as a 30 minute IV infusion every three weeks (on Day 1) of a 21-day cycle (treatment dose may be reduced due to toxicity as described in Section 4.2.1.2). Sites should make every effort to target infusion timing to be as close to 30 minutes as possible. However, given the variability of infusion pumps from site to site, a window of -5 minutes and +10 minutes is permitted (i.e., infusion time is 30

Pembrolizumab (MK-3475), [name], HUMC

minutes: -5 min/+10 min). The starting dose of pembrolizumab (MK-3475) is 200 mg, fixed dose.

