#### **4.2.1 Dose Selection/Modification**

##### **4.2.1.1 Dose Selection**

The dose amount required to prepare the pembrolizumab (MK-3475) infusion solution will be a fixed dose of 200 mg IV.

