#### **6.2.4 Evaluating Adverse Events**

An investigator who is a qualified physician will evaluate all adverse events according to the NCI Common Terminology for Adverse Events (CTCAE), version 4.03. Any adverse event which changes CTCAE grade over the course of a given episode will have each change of grade recorded on the adverse event case report forms/worksheets.

All adverse events regardless of CTCAE grade must also be evaluated for seriousness.

Table 11 Evaluating Adverse Events

An investigator who is a qualified physician, will evaluate all adverse events as to:

V4.0 CTCAE Grading	Grade 1	Mild; asymptomatic or mild symptoms; clinical or diagnostic observations only; intervention not indicated.		
	Grade 2	Moderate; minimal, local or noninvasive intervention indicated; limiting age-appropriate instrumental ADL.		
	Grade 3	Severe or medically significant but not immediately life-threatening; hospitalization or prolongation of hospitalization indicated; disabling; limiting self-care ADL.		
	Grade 4	Life threatening consequences; urgent intervention indicated.		
	Grade 5	Death related to AE		

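### Section 4.2.1.2 gives conflicting stopping instructions for Grade 4 haematologic toxicity and refers to a lower dose level that is not defined for pembrolizumab

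*Combined protocol and SAP*

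**What the plan says.** **Dose.** Section 4.2.1.1 gives a single pembrolizumab dose: "The dose amount required to prepare the pembrolizumab (MK-3475) infusion solution will be a fixed dose of 200 mg IV". The Trial Summary, Table 2 and Section 4.2.2 give the same 200 mg. The pembrolizumab paragraph of Section 4.2 adds "treatment dose may be reduced due to toxicity as described in Section 4.2.1.2".

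**Scope of Section 4.2.1.2.** The section opens on pembrolizumab alone: "Pembrolizumab must be withheld for drug-related toxicities and severe or life-threatening AEs as per Table 3 below". What it calls Table 3 is printed as Tables 3a and 3b. The title of Table 3a names pembrolizumab. The title of Table 3b is only "Dose-Modification Guidelines for Hematological Toxicity".

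**Stopping.** The last row of Table 3a, for all other drug-related toxicity, requires permanent discontinuation at Grade 4. The note beneath Table 3a reads "Permanently discontinue for any severe or Grade 3 drug-related AE that recurs or any life-threatening event". In Table 3b, Grade 4 haematologic toxicity leads to a hold. Restart is allowed on recovery to Grade 0-1 or baseline, with the option "May decrease dose to next dose level below". Its discontinuation column requires consultation with the sponsor. That column cites failure to recover within 4 weeks of the last infusion, and adds that permanent discontinuation should be considered for a severe or life-threatening event.

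**The concern.** There are two separate faults in operative dosing text. First, Section 4.2 sends the investigator to Section 4.2.1.2 for a dose reduction, and that section offers a step down to a level that does not exist for the drug it covers. Second, one section gives both a mandatory and a discretionary instruction for overlapping sets of events.

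These tables decide whether a patient stays on treatment: Section 4.8 requires discontinuation for unacceptable adverse experiences as described in Section 4.2.1. The events are foreseeable, because Section 3.2.1.4 lists cytopenias among the most common Grade 3-4 events with lenalidomide plus dexamethasone. The trial-level Grade 4 stopping rule in Section 7.1.2 counts only non-haematologic toxicity, so for haematologic events the patient-level rule carries more of the weight. Two investigators who both follow the protocol could act differently on the same event.

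**Working it through.** No arithmetic beyond a count applies. The check sets the places side by side.

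**Step 1: which dose levels are defined?**

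| Drug | Defined levels | Where | Level below the start? |
|---|---|---|---|
| Pembrolizumab | 200 mg (1 level) | 4.2, 4.2.1.1, 4.2.2 | None |
| Lenalidomide | 25, 15, 10, 5 mg (4 levels) | Table 6 | Yes |
| Dexamethasone | 40, 20, 10 mg (3 levels); 20, 10, 4 mg if older than 75 | 4.2.1.4 | Yes |

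For pembrolizumab, a next level down has nothing to refer to. The cross-reference in Section 4.2 is therefore empty as printed.

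**Step 2: which drug does Table 3b govern?** The title does not say. Three things point to pembrolizumab: the table sits in the section that covers pembrolizumab; it counts time from the last infusion, and pembrolizumab is the only infused trial drug; and lenalidomide has its own platelet and neutrophil tables (Tables 4 and 5). This is a strong inference, but the protocol does not state it.

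Reading Table 3b as a lenalidomide table creates a different conflict. Table 3b does not hold treatment at Grade 3. Section 4.2.1.3.1 covers Grade 3 or 4 neutropenia, and its Table 5 interrupts lenalidomide when neutrophils fall below 1,000/mcL.

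**Step 3: what happens to a drug-related haematologic event?**

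| Event | Table 3a, last row | Note to Table 3a | Table 3b |
|---|---|---|---|
| Grade 4, not named in Table 3a | Discontinue permanently | Depends on whether the event is life-threatening | Hold; may restart on recovery |
| Judged life-threatening | Discontinue permanently if Grade 4 | Discontinue permanently | Discontinuation to be considered |

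The first line conflicts on grade alone, through the last row of Table 3a, which has no written exception for haematologic events. The second line conflicts through the note, whatever view is taken of how Grade 4 relates to life-threatening. No sentence gives any of the three precedence.

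**Step 4: is Grade 4 the same as life-threatening here?** Not throughout. Table 11 in Section 6.2.4 describes Grade 4 as "Life threatening consequences; urgent intervention indicated". The seriousness row of the same table defines a life-threatening event by the investigator's view that the patient is at immediate risk of death. The two lines in step 3 therefore have to be kept apart.

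**The case against.** The strongest reply is that Table 3b is the specific rule for haematologic events and so displaces the general row and the note. Table 3a already contains specific departures: hypothyroidism up to Grade 4 continues on pembrolizumab, and hyperglycaemia of Grade 3-4 with evidence of beta cell failure is held and later resumed. The word other in the last row can be read as excluding toxicities that have their own table. If the note overrode every Grade 4 entry, Table 3b's restart entries would have no function. This is a fair account of what may have been intended, but it is not written. It also does not reconcile the note with Table 3b for an event that is actually life-threatening, where both speak to the same category.

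A reader might go further and infer three things that the documents do not support:

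- **That every Grade 4 haematologic event must stop permanently under the note.** The note turns on life-threatening events, and step 4 shows this is not simply Grade 4.
- **That Table 3b forces a restart at an undefined dose.** The decrease is optional. The fault is that an investigator who takes the option finds no dose defined.
- **That every patient with a Grade 4 haematologic event is affected.** Cytopenias judged related to lenalidomide have their own instructions in Tables 4 and 5, and attribution decides which rule is reached.

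The sponsor consultation in Table 3b's discontinuation column may limit divergent handling, but it does not say which rule is to be applied. The restart-dose column also carries a footnote marker with no matching note beneath Table 3b; the only footnote 1 in the section concerns liver metastasis. A note lost in text extraction cannot be ruled out, so nothing here rests on its absence.

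**Conclusion.** This is an internal inconsistency in treatment-stopping rules, and it should be corrected. Two parts stand: a reference to a reduced pembrolizumab dose that is not defined, and mandatory against discretionary discontinuation for Grade 4 and for life-threatening haematologic events, with no order of precedence.

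The first part assumes that Table 3b governs pembrolizumab, which is strongly implied but not stated. If it governs something else, the cross-reference in Section 4.2 is still empty. The second part concerns drug-related events that fall under both tables.

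The documents give no expected number of such events, so the frequency is unknown. The fault concerns conduct and patient safety; it does not alter the sample size, the decision rule or the error rates. This review takes no view on which rule or dose is right.

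**What to change.** The sponsor must reconcile Table 3b with the pembrolizumab paragraph of Section 4.2, Section 4.2.1.1, the last row of Table 3a and the note beneath it. The amendment should:

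1. Name the drug or drugs that Table 3b governs.
2. Resolve the references to dose reduction, in Section 4.2 and in Table 3b, so that they agree with the dose levels the protocol defines.
3. State which instruction applies to a Grade 4 haematologic event and which to a life-threatening one, whether or not the two are handled alike, and which text prevails where tables overlap.

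The cost is table and cross-reference wording in a protocol amendment. No statistical section needs to change.
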